8.3 Determination of Sample Size

The primary endpoints for the study are (1) PSA response rate, which is defined as the proportion of subjects achieving a $\geq 50\%$ decline in PSA at or within 9 weeks of starting Sacituzumab Govitecan. Prior published data from retrospective studies report PSA response rates ($\geq 50\%$ decline) in 20-30% of subjects on 2nd line AR directed therapy after progression on a 1st line agent in the pre-docetaxel setting (3-8), (2) and the 6-month rPFS rate. The response rate appears higher with cytotoxic chemotherapy. Although data are limited in the pre-docetaxel setting, retrospective studies in the post-docetaxel setting suggest patients with prior response to abiraterone are more likely to respond to second line enzalutamide (9-11). The familywise type I error for the two primary endpoints of the study is one-sided 0.05 and a Bonferroni adjustment for evaluating two primary endpoints will be applied that each endpoint will be tested at the one-sided 0.025 (0.05/2) significance level. A PSA response rate of 20% or less will be considered as unacceptably low. A PSA response rate of 40% or more, on the other hand, will be considered sufficient evidence to consider further clinical trial investigation. Hence, the null hypothesis that the PSA response rate is 20% will be tested against the alternative hypothesis that the PSA response rate is 40%. A sample size of 45 evaluable subjects for PSA response (defined as subjects who received at least 1 dose of Sacituzumab Govitecan and have at least 1 post-dose assessment of PSA) is required to detect an increase in the PSA response rate from 20% to 40% with 87% power at the one-sided exact test with a significance level of 0.025. Analogously, a 6-month rPFS rate of 20% or less will be considered as unacceptably low and 40% or more considered sufficient evidence. Again a sample size of 45 evaluable subjects (for assessing 6-month PFS rate) is required to detect an increase in the 6-month rPFS rate from 20% to 40% with 87% power at the one-sided 0.025 significance level. The following table shows the probabilities for rejecting the null hypothesis with a sample size of 45 evaluable subjects, assuming that the true PSA response/6-month rPFS rates range between 35-50%.

Table 10. Attainable power levels with a sample size of 45 evaluable subjects

True PSA response/6-months PFS rate	Probability of rejecting null hypothesis
35%	68%
40%	87%
45%	96%
50%	>99%

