Hence, a sample size of 45 evaluable subjects will provide between 68-99% power to detect a true PSA response rate or 6-month rPFS rate between 35-50% at the one-sided 0.025 significance level.

A sample size of 45 subjects will also be adequate for estimating toxicity rates with sufficient accuracy. Specifically, toxicity rates will be estimated with a standard error of less than 8% and the corresponding 95% confidence intervals will be no wider than 30%.

In order to account for unevaluable (for assessing PSA response or 6-month rPFS rate) subjects, 55 subjects in total will be enrolled.

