8.4.3 Efficacy Analysis

The Efficacy Analysis Set will consist of all subjects who receive at least 1 dose of Sacituzumab Govitecan and have at least 1 post-dose assessment of PSA; and/or 1 post-dose radiographic assessment for subjects with evaluable and/or measurable metastases at screening, 1 post-dose assessment of metastatic disease will be required. Subjects who

discontinue study participation early so they do not meet criteria for inclusion in the efficacy analysis set can be replaced.

Changes in PSA will be compared to baseline and maximal change from baseline and change at Week 9 (e.g., end of Cycle 3) will also be determined, as will duration of response. Maximum change in soft tissue lesions as seen on CT or MRI of the chest, abdomen and pelvis, as well as changes on bone scintigraphy according to the PCWG2 criteria will also be compared to baseline, and summarized.

A subgroup efficacy analysis will be conducted in the group of patients who continued single agent ARSI in combination with Sacituzumab Govitecan.

Definition and analysis of primary efficacy endpoint:

PSA response rate: Subjects who achieve $\geq 50\%$ PSA decline at or before 9 weeks of therapy with Sacituzumab Govitecan are considered to have responded. PSA responses will be analyzed by descriptive statistics and summarized in tabular format (frequency tables). The overall PSA response rate will be reported along with the corresponding 95% confidence interval which will be constructed using the Wilson score method.

6-month rPFS rate: Proportion of subjects remaining alive and progression free (using PCWG2 criteria) 6 months from time of starting treatment as estimated by the Kaplan-Meier method. The point estimate of the 6-month rPFS rate will be reported along with the corresponding two-sided 95% confidence interval.

Definition and analysis of secondary efficacy endpoints:

- i. *Median rPFS.* The probability distribution of PFS will be estimated using the Kaplan-Meier method. The median will be estimated from this distribution. Subjects who have not died or progressed (using PCWG2 criteria) will be censored at the date of last assessment.
- ii. *Median OS.* OS is the duration from start of treatment until death from any cause. The probability distribution of OS will be estimated using the Kaplan-Meier method. The median will be estimated from this distribution. Subjects who have not died will be censored at the date of last contact.

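### The 95% Wilson interval planned for the PSA co-primary does not match the exact test in 8.3: at 8 of the 11 evaluable sizes from 45 to 55, one response count puts the interval above 20% although the test fails.

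*Combined protocol and SAP*

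**What the plan says.** Section 8.3 (Determination of Sample Size) splits a one-sided familywise 0.05 between the two primary endpoints, so that "each endpoint will be tested at the one-sided 0.025 (0.05/2) significance level". For PSA response the null rate is 20% and the alternative 40%. "A sample size of 45 evaluable subjects for PSA response" is said to detect that difference "with 87% power at the one-sided exact test with a significance level of 0.025". To allow for unevaluable subjects, "55 subjects in total will be enrolled". For PSA, evaluable means at least one dose and at least one post-dose PSA.

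Section 8.4.3 (Efficacy Analysis) describes the PSA analysis as descriptive, with frequency tables, and then says: "The overall PSA response rate will be reported along with the corresponding 95% confidence interval which will be constructed using the Wilson score method". It does not repeat the exact test, give a critical count, or say which output governs if the test and the interval disagree. The same Wilson wording is used for toxicity rates in 8.4.2 and for overall response among the secondary endpoints, where nothing is tested.

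**The concern.** A two-sided 95% interval invites comparison with a one-sided 0.025 test: if its lower limit is above 20%, a reader will take 20% as excluded. That reading is safe only if the interval is the inversion of the test that was declared. The Wilson interval inverts the score test, which uses a normal approximation with the null variance. The exact binomial test is somewhat stricter at many sample sizes, so the plan carries two slightly different boundaries for one primary endpoint. What is at stake is a final report in which the interval for a primary endpoint lies wholly above 20% although the declared test did not reject, with nothing in 8.4.3 to tell the reader which one counts.

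**Working it through.** **Inputs.** From 8.3: null rate 0.20, alternative 0.40, one-sided 0.025, 45 evaluable, 55 enrolled. From 8.4.3: 95% Wilson score interval. Two assumptions are mine: the interval is two-sided and has no continuity correction, since 8.4.3 states neither for PSA.

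**The plan's own figure.** At n = 45 the exact critical count is 15: P(X ≥ 15 | 45, 0.20) = 0.02499, whereas P(X ≥ 14) = 0.0521. Exact power is then P(X ≥ 15 | 45, 0.40) = 85.7%, close to the stated 87%. Table 10 as a whole fits a normal approximation with null variance better:

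power = Φ{[(p − 0.2)√45 − 1.96√0.16] / √(p(1 − p))}

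| True rate | Table 10 | Normal approximation | Exact test |
|---|---|---|---|
| 35% | 68% | 67.9% | 64.7% |
| 40% | 87% | 87.2% | 85.7% |
| 45% | 96% | 96.4% | 95.9% |
| 50% | >99% | 99.3% | 99.2% |

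**The two boundaries.** For each n, the exact boundary is the smallest x with P(X ≥ x | n, 0.20) ≤ 0.025. The Wilson boundary is the smallest x whose lower limit exceeds 0.20, where, with p̂ = x/n and z = 1.96,

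lower limit = [p̂ + z²/2n − z√(p̂(1 − p̂)/n + z²/4n²)] / (1 + z²/n).

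| n | Exact needs | Wilson excludes 20% from | Wilson lower limit at that count | Exact one-sided p at that count |
|---|---|---|---|---|
| 45 | 15 | 15 | 21.4% | 0.0250 |
| 46 | 16 | 15 | 20.9% | 0.0304 |
| 47 | 16 | 15 | 20.4% | 0.0366 |
| 48 | 16 | 16 | 21.7% | 0.0210 |
| 49 | 17 | 16 | 21.2% | 0.0256 |
| 50 | 17 | 16 | 20.8% | 0.0308 |
| 51 | 17 | 16 | 20.3% | 0.0368 |
| 52 | 17 | 17 | 21.5% | 0.0215 |
| 53 | 18 | 17 | 21.1% | 0.0259 |
| 54 | 18 | 17 | 20.7% | 0.0310 |
| 55 | 18 | 17 | 20.3% | 0.0367 |

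The boundaries differ at 8 of the 11 sizes, each time by one responder and each time with Wilson the more lenient.

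**One case in full, 17/55.** p̂ = 0.3091. The score statistic is (0.3091 − 0.20)/√(0.16/55) = 0.1091/0.0539 = 2.02, above 1.96. The Wilson limits are (0.3440 ∓ 0.1270)/1.0698, that is 20.3% and 44.0%. The exact test gives P(X ≥ 17 | 55, 0.20) = 0.037, so it does not reject; 18 responders are needed. Likewise 16/50 has a Wilson interval of 20.8-45.8% and exact p = 0.031.

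**How often.** At each discordant size only the single count in the table conflicts. Over the eight sizes its probability is 1.4-2.0% at a true rate of 20%, 11-12% at 30% and 4-7% at 40%.

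**Level.** The exact rule has level at or below 0.025 at every size. If the Wilson limit were used as the rule instead, its level would be the p-value in the last column: 0.026-0.037 at the eight sizes.

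**Check of the remedy.** The Clopper-Pearson lower limit reaches 20% at exactly the exact-test critical count for every n from 45 to 55 (15, 16, 16, 16, 17, 17, 17, 17, 18, 18, 18), so no conflicts remain.

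**The case against.** The strongest reply is that nothing in the documents makes the Wilson interval the decision rule. Section 8.3 names the test; 8.4.3 calls its summary descriptive and uses an interval that it also uses where nothing is tested. This stands. A reader might infer that the plan fails to hold its 0.025 per-endpoint level, or that the Bonferroni split is broken, with a worst-case sum of 0.037 + 0.025 = 0.062. The documents do not support that: followed as written, the exact test keeps its level at every sample size.

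A reader might also take 8 of 11 to mean that a contradictory result is likely. It counts sample sizes, not outcomes. Only one response count conflicts at each of those sizes, and at the planned 45 none does.

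The final number is also uncertain. Section 4.1 says enrolment is up to 55, the extra subjects cover unevaluability for either endpoint, and the efficacy set in 8.4.3 carries a radiographic clause that could reduce it. So 46-55 is possible rather than established. A smaller number is no safeguard, however: 40, 42 and 43 conflict as well.

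Two further points have force. With a continuity correction only 49 and 53 would conflict. And since Table 10 fits the normal approximation, Wilson may match the method behind the sizing table. But the text of 8.3 says exact, so this is a further reason to state which test applies. Wilson is a sound interval for a proportion in its own right; the difficulty lies only in pairing it with an exact test.

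**Conclusion.** The point holds as a mismatch between test and reported interval on a primary endpoint, not as a failure of error control. It can arise at 8 of the 11 evaluable sizes from 45 to 55, at one response count in each, and always in the direction of an interval above 20% with a failed test. It is least likely if the true rate is 20% and most relevant if the truth lies between the two hypotheses, where the chance reaches about one in nine. The result rests on a two-sided 95% Wilson interval without continuity correction and on an evaluable number other than 45, 48 or 52 within that range. It is a modest inconsistency, worth settling before results are seen because settling it costs almost nothing.

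**What to change.** In 8.4.3, state that the one-sided exact binomial test of 8.3 at 0.025 decides the PSA co-primary at the actual evaluable number, and report the PSA response rate with a two-sided 95% Clopper-Pearson interval. Keep Wilson for toxicity and secondary rates. The sentence on which test decides would by itself remove the ambiguity; the change of interval also stops the report from showing an interval and a test that disagree.

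The cost is a line or so of wording and a slightly wider interval: for 17/55, 19.1-44.8% instead of 20.3-44.0%. Sample size, conduct and data collection are unaffected.

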5.7 Long-Term Follow-Up

After completing the end of treatment evaluation, follow-up continues for subjects who have not progressed with assessments including PSA, bone scan and/or CT scans performed every 3 months or per standard of care for up to 2 years from initiation of study therapy or until progression of disease or initiation of other treatment. Modalities of disease assessment at baseline will be used at subsequent response evaluations for determination of response and/or disease progression.

Adverse events and concomitant medications reported at any follow-up visits will include outcome of any ongoing unresolved events, new events attributed to the study treatment, deaths, hospitalizations, and infectious episodes requiring prescription or IV anti-infectives or GI toxicity. Follow-up for treatment related toxicities which may include physical exam, CBC and chemistries will be required till resolution or stabilization of the toxicity.

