5.8 Criteria for Removal from Protocol Treatment

Every effort should be made to keep subjects on study drug for a minimum of 9 weeks (i.e., 3 cycles) unless withdrawal of informed consent, the presence of significant toxicity, clear progression of neoplastic disease, or any other reason for the removal from study as outlined in this section. Per the PCWG2 guidelines, "in the absence of clinically-compelling indicators of disease progression, early changes (within 9 weeks) in indicators such as serum PSA, patient-reported pain, and radionuclide bone scan should be ignored". With respect to bone scan changes, 72% of the apparent disease progressions, in the abiraterone acetate plus prednisone vs. placebo plus prednisone registration trial, proved to be responders and were able to continue therapy. In contrast, unequivocal signs of disease progression such as spinal cord compression or pain requiring a change in therapy would require discontinuation of Sacituzumab Govitecan prior to 9 weeks (i.e., before completing Cycle 3).

Subjects who require palliative radiotherapy for focal symptom relief may remain on study as long as the treating investigator feels they are deriving benefit from Sacituzumab Govitecan 2 and the radiotherapy is not to a target or non-target lesion recorded at baseline.

Subjects may be removed from protocol treatment under the following conditions:

- First documentation of progressive disease or symptomatic deterioration indicating treatment failure.
 - Discontinuation is subject to the goal of not removing subjects prior to completing 9 weeks of treatment especially for the lone reason of rising PSA. Subjects with rising PSA may continue on study beyond Cycle 3 at the discretion of the investigator.

- Subjects who want to continue treatment after radiological documentation of progressive disease should notify the physician who will obtain Sponsor approval before treatment continuation.
- Unacceptable toxicity, or any AE, which in the opinion of the investigator precludes further participation in the study.

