⁷All subjects should have adverse events evaluated at least 30 days from the last dose of study drug. Follow-up for progression will be performed every 3 months or per standard of care for up to 2 years from initiation of study therapy if subjects discontinue study treatment prior to progression. For subjects coming off-treatment due to progression, follow-up is complete once AEs have been evaluated at least 30 days after the last dose of the study drug.

⁸If not performed within 30 days of End of Treatment/Progression

⁹If lab values are not within normal range on day 1 or day 8, consider repeat CBC with differential on day 15, as per MD discretion. In the case of a Grade 3 ANC subjects should be assessed weekly and for grade 4 ANC subjects should be assessed bi-weekly as per section 6.4.1.

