APPENDIX E: PROSTATE CANCER WORKING GROUP 2 (PCWG2) RESPONSE CRITERIA

The effects of Sacituzumab Govitecan will be assessed using both “control/ relieve/ eliminate” endpoints as well as “prevent/ delay” endpoints as outlined in the PCWG2 response criteria summarized in the table below.

Variable	PCWG2 (2007)
PSA	
Recognize that a favorable effect on PSA may be delayed for 9 weeks or more, even for a cytotoxic drug
 
Monitor PSA by cycle but plan to continue through early rises for a minimum of 9 weeks unless other evidence of progression
 
Ignore early rises (prior to 9 weeks) in determining PSA response
 
For control/relieve/eliminate endpoints:
 
Record the percent change from baseline (rise or fall) at 9 weeks, and separately, the maximal change (rise or fall) at any time using a waterfall plot
 
For prevent/ delay (progression): Decline from baseline: Record time from start of therapy to first PSA increase that is > 25% and > 2 ng/ml above the nadir, and which is confirmed by a second value 3 or more weeks later (i.e., a confirmed rising trend).
 
No decline from baseline: PSA progression > 25% and > 2 ng/ml after 9 weeks

Soft-tissue lesions	
For control/relieve/ eliminate endpoints: Use RECIST with caveats:
 
Only report changes in lymph nodes that were > 2 cm in diameter at baseline
 
Record changes in nodal and visceral soft tissue sites separately
 
Record complete elimination of disease at any site separately
 
Confirm favorable change with second scan
 
Record changes using waterfall plot
 
For prevent/ delay endpoints (progression): Use RECIST criteria for progression, with additional requirement that progression at first assessment be confirmed by a second scan 6 or more weeks later.
 
Note that for some treatments, a lesion may increase in size before it decreases

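### Men removed at an unconfirmed first-scan progression have no confirmatory scan due and, on the only rPFS censoring rule given, are censored at about week 9, which can bias the co-primary 6-month rPFS rate upward

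*Combined protocol and SAP*

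**What the plan says.** - **Endpoint (8.4.3).** The 6-month rPFS rate is estimated by Kaplan-Meier, using PCWG2 criteria, with a two-sided 95% confidence interval. That paragraph has no censoring rule. The only rPFS rule stands under the secondary endpoint, median rPFS: "Subjects who have not died or progressed (using PCWG2 criteria) will be censored at the date of last assessment".
- **Test (8.3).** The decision frame is "a 6-month rPFS rate of 20% or less will be considered as unacceptably low and 40% or more considered sufficient evidence", and "each endpoint will be tested at the one-sided 0.025 (0.05/2) significance level".
- **Confirmation (Appendix E).** For soft tissue there is an "additional requirement that progression at first assessment be confirmed by a second scan 6 or more weeks later". Bone has a parallel requirement at the first reassessment. Progression is dated to the first scan that shows the change.
- **Removal (5.8).** The conditions under which a man may be removed include "First documentation of progressive disease or symptomatic deterioration indicating treatment failure". Continuing after radiological progression needs sponsor approval.
- **Imaging (5.3).** Nine-weekly rescans are for men who are still progression-free on study.
- **Follow-up (Appendix B).** Footnote 7: "For subjects coming off-treatment due to progression, follow-up is complete once AEs have been evaluated", which is at least 30 days after the last dose. Footnote 8 asks for end-of-treatment imaging only if none was done within 30 days.
- **Long-term follow-up (5.7).** For men who have not progressed, assessments run for up to 2 years or "until progression of disease or initiation of other treatment".

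**The concern.** Two meanings of progression are in play. For the analysis, a first-scan finding is not progression until a later scan confirms it. For conduct, the same finding can be the progression that ends treatment and follow-up. A man caught between the two has no event and no further scan, so he leaves the risk set at about week 9. Kaplan-Meier then credits him with the prospects of the men who had no finding at that scan.

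If he was in fact progressing, that credit is wrong and the 6-month rate is too high. This is a single-arm test against a fixed 20%, so no control arm shares the bias, and the endpoint is one of two that can each declare the trial positive.

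**Working it through.** **1. Is a confirmatory scan due?** On the nominal calendar (Appendix B, 5.6):

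- Cycle 3 Day 1 is study day 43, so the last dose before the first scan (Cycle 3 Day 8) is day 50 and the scan (Cycle 3 Day 15) is day 57.
- The End of Treatment visit is 30 to 37 days after the last dose: days 80 to 87.
- That is 23 to 30 days after the scan, so footnote 8 requires no new imaging.
- The earliest qualifying confirmatory scan is day 57 + 42 = day 99, after footnote 7 can already have closed follow-up.

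A man removed at the first scan therefore has no confirmatory scan scheduled.

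**2. The plan's own figure.** Section 8.3 states it can "detect an increase in the 6-month rPFS rate from 20% to 40% with 87% power at the one-sided 0.025 significance level", with 45 evaluable men. The normal approximation is Φ[(√45 × 0.20 − 1.96 × √(0.2 × 0.8)) / √(0.4 × 0.6)] = Φ[(1.3416 − 0.7840) / 0.4899] = Φ(1.138), about 87%. The stated power is reproduced. An exact binomial test needs at least 15 of 45 and gives alpha 0.02499 and power 85.7%.

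**3. Effect of the censoring.** Assumptions:

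- constant hazard, with three equal scan intervals (about weeks 9, 18 and 27) and the third scan taken as 6 months;
- u is the share of true first-scan progressors who are censored at that scan;
- events precede censorings at the same time;
- success means that the lower two-sided 95% limit (Greenwood, log-log) exceeds 20%. Section 8.4.3 does not name the interval method, so this rule is assumed.

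With a true 6-month rate S, the per-interval survival is q = S^(1/3). The Kaplan-Meier limit is

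KM = [1 − (1 − q)(1 − u)] × q² = S + u(1 − q)q².

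For S = 0.20, q = 0.5848, 1 − q = 0.4152 and q² = 0.3420. About 45 × 0.4152 = 18.7 men progress by the first scan, and KM = 0.20 + 0.142u. For u = 0.25: (1 − 0.4152 × 0.75) × 0.3420 = 0.6886 × 0.3420 = 0.2355.

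False-positive rates come from 40,000 simulated trials of 45 men per setting.

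| u (assumed) | Men censored (18.7 × u) | KM estimate, true rate 20% | False-positive rate |
|---|---|---|---|
| 0% | 0 | 20.0% | 2.5% |
| 10% | 1.9 | 21.4% | 3.3% |
| 25% | 4.7 | 23.5% | 6.4% |
| 50% | 9.3 | 27.1% | 14.2% |
| 100% (bound) | 18.7 | 34.2% | 33.9% |

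For S = 0.40, (1 − q)q² = 0.2632 × 0.5429 = 0.143. The estimate rises to 41.4% at u = 10% and 47.1% at u = 50%.

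**The case against.** **The rule is written for another endpoint, and the text is silent on unconfirmed findings.** Both are true. The censoring sentence belongs to median rPFS, and an analyst could count an unconfirmed first scan as an event. But no other rPFS rule exists, so the primary endpoint has either this rule or none. In an open-label trial, that choice should not wait until the data are seen.

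**Consistent use of PCWG2 removes the problem.** On that reading, a man with an unconfirmed scan has not progressed, may stay on treatment and is rescanned. If he stops, 5.7 keeps imaging him every 3 months. Section 5.8 says may, not must, and Appendix E does call for a confirmatory bone scan. This is a fair reading, and it means the loss is possible rather than systematic. It does not remove the conflict: 5.8 names first documentation as a ground for removal, and 5.3 and footnote 7 do not distinguish confirmed from unconfirmed progression.

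**Flare.** Section 5.8 reports that in one registration trial 72% of apparent bone-scan progressions proved to be responders. Censoring men with flare does not inflate the rate, and counting them as events would bias it downward. This stands for bone. The cited figure does not concern soft tissue.

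**Men who move to other treatment.** A reader might infer that they are lost in the same way, because 5.7 stops assessments at the switch. The documents do not support that as a comparable defect. Section 5.6 repeats the End of Treatment procedures when another treatment starts, including imaging if none was done within 30 days. Nothing censors at new therapy, and a later known death still counts. Bias would also require switching to be informative. No figure is put on this.

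**Conclusion.** The gap is real. Followed as written, the removal and follow-up passages can leave a first-scan progressor without the scan that Appendix E needs, and the only stated rule then censors him at about week 9. If the censored men are truly progressing, the estimate rises by about 1.4 percentage points for each 10% of first-scan progressors affected. Losing about five of 45 men in this way would take the false-positive rate from 2.5% to about 6.4%.

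The size depends on assumed fractions, a constant hazard and a log-log limit. Only the truly progressing men contribute to u.

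Two stronger readings are tempting, and neither is supported:

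- **That this censoring must always inflate the rate.** Direction depends on whether the censored men are at higher risk than those who remain, and flare can shrink or reverse the bias.
- **That the 0.025 level is lost.** At 10% affected the false-positive rate is 3.3%. With none affected the level holds. The documents do not say how many men would be affected.

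**What to change.** 1. **Reconcile 5.3, 5.8 and Appendix B footnotes 7 and 8 with Appendix E.** A man whose only progression is an unconfirmed first scan should not count as having completed follow-up. Collect his later standard-of-care scans and any death to 6 months. This concerns data collection only, not whether he stays on treatment.
2. **State the censoring rule for the primary 6-month rate in 8.4.3.** Pre-specify that soft-tissue progression at the first reassessment is an event at that scan date when no confirmatory scan is obtained, and declare this as a departure from Appendix E. Report the rate twice: with all unconfirmed first-scan findings, bone included, counted as events, and with all of them censored.
3. **Add a sensitivity analysis only** that counts the start of other anticancer treatment, or symptomatic deterioration, as an event.

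The cost is a small protocol amendment to the follow-up wording, new text in 8.4.3 and two extra analysis runs. The downside is a possibly slightly conservative estimate if some unconfirmed soft-tissue changes would not have been confirmed. Bone flare enters only the reported range, so it does not drive the primary result downward.
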